Symptomatic endocrinopathy (e.g., hypophysitis, adrenal insufficiency, hypothyroidism, hyperthyroidism)	 Endocrinology consultation Rule out infection/sepsis and other alternative causes with appropriate cultures and imaging Evaluate hormone levels (e.g. ACTH, cortisol, FSH/LH, TSH, free T4, testosterone/estrogen), metabolic panel (e.g. Na, K, CO2, glucose), and imaging (e.g. brain MRI) as clinically indicated Initiate hormone replacement therapy as appropriate Consider steroids (methylprednisolone 1 to 2 mg/kg/d or equivalent) in case of sever hypophysitis or thyrotoxicosis Replacement of appropriate hormones may be required as the steroid dose is tapered Hypophysitis with clinically significant adrenal insufficiency and hypotension, dehydration, and electrolyte abnormalities (such as hyponatremia and hyperkalemia) constitutes adrenal crisis Consider a beta-blocker in case of severe hyper-thyroidism. Consider hospitalization (e.g. in case of severe adrenal insufficiency/crisis), fluid replacement, and other supportive measures as clinically be initiated 	 Interrupt spartalizumab/LAG525 until symptomatic recovery to mild (i.e., grade 1) or no symptoms, and controlled with hormone replacement therapy Hypothyroidism may be managed with replacement therapy without treatment interruption (unless life-threatening) Permanently discontinue for life-threatening (Grade 4) endocrinopathies (i.e., hyperthyroidism, adrenal insufficiency, hypophysitis) or recurring severe/life-threatening events not controlled by hormone replacement therapy

Endocrine events (NCI-CTCAE v5.0)				
Grade	Recommended Adverse Event management guidelines	Mandatory Dose Modification requirements		
Autoimmune diabetes (Grade 3 or symptomatic hyperglycemia) Autoimmune diabetes (Grade 4 hyperglycemia or life-threatening complications)	 Initiate anti-glycemic therapy (i.e., insulin) as medically indicated and monitor glucose levels regularly until metabolic control is achieved Evaluate for ketoacidosis as medically indicated Consultation with endocrinologist Consider hospitalization (e.g. in case of ketoacidosis) 	Interrupt spartalizumab/LAG525 until recovery to grade 1 or baseline Permanently discontinue spartalizumab/LAG525 in case of recurring severe/life-threatening events not controlled by antiglycemic therapy		

Table 6-9 Criteria for dose interruption and re-initiation of LAG525 and spartalizumab treatment for infusion-related reactions

Infusion reaction (NCI-CTCAE v5.0)				
Grade	Recommended Adverse Event management guidelines	Mandatory Dose Modification requirements		
Grade 1 Mild reaction; infusion interruption not indicated; intervention not indicated	 Increase monitoring of vital signs/pulse oximetry as medically indicated until the participant is deemed medically stable in the opinion of the investigator Consider slowing infusion rate until recovery of symptoms 	Continue spartalizumab/LAG525		
Grade 2 Requires infusion interruption but responds promptly to symptomatic treatment (e.g., antihistamines, NSAIDS, narcotics, i.v. fluids); prophylactic medications indicated for < =24 hrs	Stop Infusion and keep line open Additional medical therapy as per local institutional guidelines that may include:	Permanently discontinue spartalizumab/LAG525 in case of recurring infusion reaction despite adequate premedication and prolonged infusion/slow infusion rate		

Infusion reaction (NCI-CTC	AE v5.0)	
Grade	Recommended Adverse Event management guidelines	Mandatory Dose Modification requirements
	participant is deemed medically stable. If symptoms resolve, the infusion may be restarted at 50% of the original infusion rate Premedicate participants approximately 1.5 hrs prior to next infusion of spartalizumab/LAG525 with: Diphenhydramine (50 mg po or equivalent) Acetaminophen (500-1000 mg po or equivalent) Or as per local institutional guidelines	
Grade 3: Prolonged (i.e., not rapidly responsive to symptomatic medication and/or brief interruption of infusion); recurrence of symptoms following initial improvement; hospitalization indicated for other clinical sequelae (e.g., renal impairment, pulmonary infiltrates) Grade 4: Life-threatening; pressor or ventilatory support indicated	Stop Infusion Additional medical therapy as per local institutional guidelines that may include: i.v. fluids Antihistamines NSAIDS Acetaminophen Narcotics Oxygen Corticosteroids Epinephrine Close monitoring of vital signs, pulse oximetry and ECG as medically indicated until the participant is deemed medically stable. Hospitalization as indicated	Permanently discontinue spartalizumab/LAG525

Table 6-10 Criteria for dose interruption and re-initiation of LAG525 and spartalizumab treatment for "other" potential immune-related AEs of special interest

Other immune mediated events- including but not limited to Autoimmune neuropathy, Demyelinating polyneuropathy, Guillain-Barre syndrome, Myasthenia gravis- like syndrome, Non-infectious myocarditis, pericarditis, pancreatitis, and Grade 3 Fatigue with rapid onset in absence of disease progression, encephalitis, vasculitis, myositis, hemolytic anemia, uveitis

uveitis		T
Grade	Recommended Adverse Event management guidelines	Mandatory Dose Modification requirements
Mild (Grade 1)	Provide symptomatic treatment evaluate/monitor adequately	Continue spartalizumab/LAG525
Moderate (Grade 2)	 Ensure adequate evaluation to confirm etiology or exclude other causes Provide symptomatic treatment Systemic corticosteroids may be indicated Consider biopsy for confirmation of diagnosis. A specialist should be consulted 	Consider interruption of spartalizumab/LAG525 until recovery to ≤ Grade 1 or baseline
Severe (Grade 3)	 Initiate systemic corticosteroids (prednisone or equivalent) at a dose of 1-2 mg/kg/d or equivalent) and other therapies as appropriate Monitor closely and consult with a specialist 	 Interrupt spartalizumab/LAG525 until recovery to ≤ Grade 1 or baseline May restart spartalizumab/LAG525 treatment at the same dose and schedule
		 2nd occurrence: Permanently discontinue spartalizumab/LAG525
Grade 4	Hospitalization and consult with specialist	Permanently discontinue spartalizumab/LAG525
Guillain-Barre Severe peripheral or autonomic neuropathy, or transverse myelitis	Hospitalization and consult with specialist	Permanently discontinue spartalizumab/LAG525
Encephalitis or aseptic meningitis	 Rule out infectious or other causes of moderate to severe neurologic deterioration, and consult with specialist If other etiologies are ruled out, administer corticosteroids at a dose of 1 to 2 mg/kg/day prednisone equivalents 	Permanently discontinue spartalizumab/LAG525
Myasthenia gravis	Consult with specialist	Grade 2

Other immune mediated events- including but not limited to Autoimmune neuropathy, Demyelinating polyneuropathy, Guillain-Barre syndrome, Myasthenia gravis- like syndrome, Non-infectious myocarditis, pericarditis, pancreatitis, and Grade 3 Fatigue with rapid onset in absence of disease progression, encephalitis, vasculitis, myositis, hemolytic anemia, uveitis

Recommended Adverse Event management guidelines Consider pyridostigmine and systemic corticosteroids	Mandatory Dose Modification requirements • Interrupt PDR001 until
	 Interrupt PDR001 until
 (prednisone or equivalent) at a dose of 1-2 mg/kg/d; other therapies as appropriate (e.g. i.v. lg) Hospitalization in case of severe cases 	recovery to ≤ Grade 1 or baseline Grade ≥3 • Permanently discontinue spartalizumab/LAG525
Urgent cardiology consult is essential to initiate high dose systemic corticosteroids (prednisone or equivalent) (Mahmood et al 2018, Brahmer et al 2018)	Permanently discontinue spartalizumab/LAG525
 Evaluate for pancreatitis (clinical assessment, abdominal imaging and/or MRCP as appropriate) PDR001 may be continued in case of asymptomatic, isolated enzyme elevations without evidence for pancreatitis Initiate steroids in case of ≥ grade 2 acute pancreatitis 	Grade 2 acute pancreatitis: Interrupt PDR001 until recovery to ≤ Grade 1 or baseline Grade ≥3 acute pancreatitis: Permanently discontinue spartalizumab/LAG525
Consult with specialist Consider systemic corticosteroids and other therapies as appropriate (e.g. transfusion) per local institutional guidelines	Permanently discontinue spartalizumab/LAG525
Consult with ophthalmologist	Grade 2 Interrupt PDR001 until recovery to ≤ Grade 1 or baseline Grade 3 and 4 Permanently discontinue
	a dose of 1-2 mg/kg/d; other therapies as appropriate (e.g. i.v. lg) • Hospitalization in case of severe cases Urgent cardiology consult is essential to initiate high dose systemic corticosteroids (prednisone or equivalent) (Mahmood et al 2018, Brahmer et al 2018) • Evaluate for pancreatitis (clinical assessment, abdominal imaging and/or MRCP as appropriate) • PDR001 may be continued in case of asymptomatic, isolated enzyme elevations without evidence for pancreatitis • Initiate steroids in case of ≥ grade 2 acute pancreatitis • Consult with specialist Consider systemic corticosteroids and other therapies as appropriate (e.g. transfusion) per local institutional guidelines

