5.1 Inclusion criteria

Participants eligible for inclusion in this study must meet all of the following criteria:

- 1. Patient is an adult \geq 18 years old at the time of informed consent, and has signed informed consent before any trial related activities and according to local guidelines
- 2. Patient has advanced (loco-regionally recurrent not amenable to curative therapy or metastatic) breast cancer.
- 3. Patient has an Eastern Cooperative Oncology Group (ECOG) performance status of 0 or 1.
- 4. Patient has adequate bone marrow and organ function as defined by the following laboratory values (as assessed by central laboratory for eligibility):
 - Absolute neutrophil count $\geq 1.5 \times 10^9/L$
 - Platelets $> 100 \times 10^9/L$
 - Hemoglobin $\geq 9.0 \text{ g/dL}$
 - Creatinine clearance (calculated using Cockcroft-Gault formula, or measured) ≥ 40 mL/min
 - Alanine aminotransferase (ALT) < 3 x ULN, except for patients that have tumor involvement of the liver, who may only be included if ALT ≤5.0 x ULN who are excluded if ALT > 5 x ULN
 - Aspartate aminotransferase (AST) < 3 x ULN, except for patients that have tumor involvement of the liver, who may only be included if AST ≤5.0 x ULN who are excluded if AST > 5 x ULN
 - Total serum bilirubin < 1.5 ULN; or total bilirubin ≤ 3.0 × ULN with direct bilirubin within normal range of the central laboratory in patients with well documented Gilbert's Syndrome
- 5. Patient must have measurable disease, i.e., at least one measurable lesion as per RECIST 1.1 criteria (Tumor lesions previously irradiated or subjected to other loco-regional therapy will only be considered measurable if disease progression at the treated site after completion of therapy is clearly documented).
- 6. Patient progressed after adjuvant or 1 prior systemic treatment in the advanced setting. Patients with *de novo* metastatic disease are eligible if they received 1 prior line of therapy.
- 7. Patient must have received prior systemic treatment that included taxane-based chemotherapy for adjuvant or metastatic disease.
- 8. Patient must have a site of disease amenable to biopsy, and must be willing to undergo a new tumor biopsy at screening and during therapy on this study, the latter if medically feasible. Patients with an available archival tumor tissue do not need to perform a tumor biopsy at screening if patient has not received anti-cancer therapy since the biopsy was taken.

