Participants receiving spartalizumab and/or LAG525, may experience other irAEs than those listed in this document, therefore all AEs of unknown etiology associated with drug exposure should be evaluated to determine if it is possibly immune-related. In cases where the specific irAE is not listed in the tables below, the investigator should follow the guidance in Section 6.5.1.1. Investigators are encouraged to contact the Sponsor as needed to discuss cases that warrant separate discussion outside of the scope of the current instructions.

The dosing modification requirements are mandatory; however, the AE management guidelines are recommendations and can be modified according to the local practices.

General dose modification instructions:

No changes in dose of spartalizumab and/or LAG525 are allowed.

Overall AEs are to be graded according to NCI-CTCAE v5.0 (https://ctep.cancer.gov). All dose interruptions and the reason for the dose interruption must be documented in the eCRF.

Overall, participants with AEs suspected to be related to spartalizumab or LAG525 including those of potential immune-mediated etiology (irAE) may need to interrupt or permanently discontinue study treatment as outlined in Section 6.5.

Permanently discontinue spartalizumab/LAG525 for any of the following:

- 1. Any life-threatening adverse reaction (excluding endocrinopathies controlled with hormone replacement therapy).
- 2. Inability to reduce corticosteroid dose to 10 mg or less of prednisone or equivalent per day within 12 weeks. The 12 weeks' timeframe will begin from the time the irAE reaches a grade that leads to spartalizumab and or LAG525 interruption.
- 3. Persistent Grade 2 or 3 adverse reactions (excluding endocrinopathies controlled with hormone replacement therapy) that do not recover to Grade 0-1 within 12 weeks after last dose of spartalizumab/LAG525.
- 4. Any severe or Grade 3 treatment-related adverse reaction that recurs.

Table 6-3 Criteria for dose interruption and re-initiation of LAG525 and spartalizumab treatment for potential immune-related diarrhea/colitis

Diarrhea/Colitis (NCI-CTCAE v5.0)		
Grade	Recommended Adverse Event management guidelines	Mandatory Dose Modification requirements
Grade 1 (Increase of <4 stools per day over baseline; mild increase in ostomy output compared to baseline)	Symptomatic treatment (loperamide, hydration, diet) Monitor closely	May continue spartalizumab/LAG525 treatment

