Grade 2: AST or ALT >3.0 - 5.0 x ULN if baseline was normal; >3.0 - 5.0 x baseline if baseline was abnormal or bilirubin >1.5 - 3.0 x ULN if baseline was normal; >1.5 - 3.0 x baseline if baseline was abnormal (if participant meets criteria for potential drug-induced liver injury (DILI) cases refer to Section 6.5.2.1)	 Monitor hepatic laboratory tests more frequently (every 2-3 days) until returned to baseline values Rule-out alternative causes (e.g. concomitant medications, infection, disease progression) Consider prednisone (0.5-1 mg/kg/d) if liver tests worsen and/or significant symptoms 	Interrupt spartalizumab/LAG525 treatment until recovery to Grade ≤1 or baseline
Grade 3 or 4: AST or ALT >5.0xULN and/or bilirubin > 3.0x ULN	 Monitor hepatic laboratory tests more frequently (every 2-3 days) until returned to baseline values. Consult with hepatologist; consider hospitalization and liver biopsy to establish etiology Initiate treatment with steroids (prednisone 1-2 mg/kg/d or i.v. equivalent) Add prophylactic antibiotics for opportunistic infections as appropriate Once symptoms/liver tests improve to Grade ≤1, taper steroids over at least 4 weeks If no improvement or steroid refractory 	 Permanently discontinue spartalizumab/LAG525 Participants with baseline grade 2 AST/ALT value (>3.0-5.0 ULN) will discontinue spartalizumab/LAG525 treatment if value increased to grade 3 with increase >=2x baseline, or to grade 4

Abnormal liver function tests		
Severity	Recommended Adverse Event management guidelines	Mandatory Dose Modification requirements
	after 3 days, consider oral mycophenolate as per local treatment guidance Infliximab is not	
	recommended due to its hepatotoxicity potential	

^{*} Send viral serology looking for hepatitis A, B, C & CMV and rule out any potential cause of liver injury (i.e., alcohol, other medications, etc.) Note: For additional information on follow-up of potential drug induced liver injury cases, refer to Section 6.5.2.1.

Table 6-5 Criteria for dose interruption and re-initiation of LAG525 and spartalizumab treatment for potential immune-related skin events

Skin Events (NCI-CTCAE v5.0)		
Grade	Recommended Adverse Event management guidelines	Mandatory Dose Modification requirements

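### In Protocol Table 6-4, an abnormal baseline can place the same AST, ALT or bilirubin value under both the interrupt row and the permanent-discontinuation row

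*Protocol*

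**What the plan says.** Protocol Section 6.5.1.2.1 contains Table 6-4, which governs LAG525 and spartalizumab when a liver laboratory change may be immune-related.

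- **Grade 2 row.** A normal baseline is judged against ULN. For an abnormal baseline the AST/ALT band is ">3.0 - 5.0 x baseline if baseline was abnormal" and the bilirubin band is ">1.5 - 3.0 x baseline if baseline was abnormal". The mandatory action is "Interrupt spartalizumab/LAG525 treatment until recovery to Grade ≤1 or baseline".
- **Grade 3 or 4 row.** The definition is "Grade 3 or 4: AST or ALT >5.0xULN and/or bilirubin > 3.0x ULN". It has no form for an abnormal baseline. The first bullet of the mandatory action is permanent discontinuation of both antibodies.
- **Second bullet in that cell.** "Participants with baseline grade 2 AST/ALT value (>3.0-5.0 ULN) will discontinue spartalizumab/LAG525 treatment if value increased to grade 3 with increase >=2x baseline"; it adds an increase to grade 4 as a further trigger.

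The same section says of the action column: "The dosing modification requirements are mandatory". Section 6.5.1.1 adds that permanent discontinuation is obligatory wherever the tables call for it.

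Section 5.1, criterion 4, admits AST and ALT below 3 x ULN in general and up to 5.0 x ULN with liver involvement. Bilirubin must be below 1.5 x ULN, except that well-documented Gilbert's syndrome allows "total bilirubin ≤ 3.0 × ULN with direct bilirubin within normal range of the central laboratory".

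**The concern.** Two adjacent rows with different mandatory actions are measured against different references. If their ranges intersect for eligible participants, an investigator cannot comply with both, and nothing in the table says which row prevails. Two sites following the text exactly could then differ on the same laboratory value: one resumes both antibodies after recovery and the other never does.

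That bears on participant management. It also bears on exposure and on the SAP Section 2.9.1 summaries of adverse events leading to treatment discontinuation and to dose adjustment or interruption, because the category an event falls into would depend on which row the site applied.

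**Working it through.** The documents give no figure to reproduce; the check is interval arithmetic on the Table 6-4 limits. Let b be the baseline as a multiple of ULN, with b > 1 for an abnormal baseline. All values below are multiples of ULN.

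**Normal baseline.** AST/ALT: Grade 2 is above 3 to 5 and Grade 3/4 is above 5. Bilirubin: above 1.5 to 3 against above 3. Neither pair overlaps.

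**AST/ALT, abnormal baseline.** Grade 2 runs from above 3b to 5b and Grade 3/4 is above 5. The overlap runs from max(3b, 5) to 5b. It exists whenever 5b > 5, that is for every b > 1. It covers the whole Grade 2 band once 3b ≥ 5, that is from b = 5/3 = 1.67.

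| b | Grade 2 band | Also in the discontinuation row | Share of band |
|---|---|---|---|
| 1.2 | 3.6–6.0 | 5–6.0 | (6.0 − 5)/(6.0 − 3.6) = 42% |
| 1.5 | 4.5–7.5 | 5–7.5 | (7.5 − 5)/(7.5 − 4.5) = 83% |
| 2 | 6–10 | 6–10 | 100% |
| 4 | 12–20 | 12–20 | 100% |

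**Bilirubin, abnormal baseline.** Grade 2 runs from above 1.5b to 3b and Grade 3/4 is above 3. The overlap runs from max(1.5b, 3) to 3b. It exists for every b > 1 and is complete once 1.5b ≥ 3, that is from b = 2.

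| b | Grade 2 band | Also in the discontinuation row | Share of band |
|---|---|---|---|
| 1.2 | 1.8–3.6 | 3–3.6 | (3.6 − 3)/(3.6 − 1.8) = 33% |
| 1.4 | 2.1–4.2 | 3–4.2 | (4.2 − 3)/(4.2 − 2.1) = 57% |
| 2.5 | 3.75–7.5 | 3.75–7.5 | 100% |
| 3 | 4.5–9 | 4.5–9 | 100% |

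A grid in steps of 0.001 over the eligible abnormal baselines (AST/ALT up to 5, bilirubin up to 3) found an overlap at every point.

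**Who can have these baselines.** AST/ALT baselines above 1 and below 3 are eligible without liver involvement; baselines from 3 to 5 need liver involvement. Bilirubin baselines above 1 and below 1.5 are open to anyone; those up to 3.0 need Gilbert's syndrome.

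**Effect of the second bullet.** It applies only to AST/ALT with b above 3.0 and up to 5.0. Its condition on the increase can mean a value of at least 2b, or a rise of 2b and hence a value of at least b + 2b = 3b. At b = 4 these are 8 and 12. Every value in the Grade 2 band is above 3b, so it meets the condition on either reading, and it also exceeds 5. The overlap with the Grade 2 row (12–20 at b = 4) therefore remains. The bullet does not touch bilirubin or AST/ALT baselines above 1 and up to 3.0.

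**The case against.** The strongest reply has five parts.

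1. **Scope.** Section 6.5.1 confines the mandatory modifications to events suspected to be related to study drug, and the Grade 2 row itself tells the investigator to rule out other causes, including disease progression. This stands. A reader might infer that any bilirubin rise above 3.0 x ULN in a participant admitted with Gilbert's syndrome forces discontinuation. The documents do not support that, because a change attributed to Gilbert's syndrome is not a suspected drug-related event.
2. **Both rows stop dosing.** This also stands. In the overlap neither row lets the antibodies continue through the abnormality; the rows differ on re-initiation.
3. **The second bullet is an exception.** A reader might see it as contradicting the first bullet. The more natural reading is a subgroup exception, since otherwise it has no function. It is not labelled as one, however, and its threshold is ambiguous. Even as an exception it leaves the overlap between the rows in place.
4. **Other text settles it.** Section 6.5.2.1 has its own criteria for elevated baselines, but it addresses transaminases and bilirubin rising together, so isolated rises stay unresolved. SAP Section 5.3 derives laboratory grades without comparison to baseline, which governs tabulation and not dosing. One could suppose that Grade 3 tacitly means more than 5 x baseline, but the row states ULN, and the second bullet's baseline condition would then be redundant. Applying the more severe row would give one answer, but no precedence rule is stated.
5. **Timing.** The Amendment 4 summary reports 88 randomised, 85 off treatment and three still treated, all in Arm 2, with the primary analysis done. This stands and limits what a correction can now achieve.

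**Conclusion.** The inconsistency is real and confined to participants with an abnormal baseline. For a suspected treatment-related event in such a participant, Table 6-4 attaches two incompatible mandatory actions to part of the Grade 2 range at every eligible abnormal baseline. It attaches them to all of that range from b = 1.67 for AST/ALT and from b = 2 for bilirubin. The two actions conflict on whether the antibodies may be resumed.

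This rests on reading the Grade 3/4 limits as multiples of ULN, as written, and an abnormal baseline as one above ULN. The documents do not say how many participants had such baselines, so the number affected is unknown.

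A reader might infer that the problem belongs to the liver-metastasis stratum and distorts discontinuation rates there. The documents do not support that: liver metastasis is one of two stratification factors, the b = 2 example is eligible without liver involvement, and the Gilbert's allowance is not tied to metastasis.

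With three participants left on treatment at Amendment 4, this is a wording correction of modest prospective consequence. It remains relevant when earlier hepatic interruptions and discontinuations are interpreted.

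**What to change.** Reconcile the rows of Table 6-4 so that no AST, ALT or bilirubin value falls under two mandatory actions. In the same edit:

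- state whether the second bullet is an exception to the first, and whether its condition means a value of at least twice baseline or a rise of twice baseline;
- state which reference applies to an abnormal bilirubin baseline, including in participants admitted with Gilbert's syndrome.

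The sponsor's medical team must decide the reference and the action; this review takes no position on either. The cost is a wording change to one table, by amendment or investigator letter, with no new assessments.

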Grade 2 (Increase of 4 - 6 stools per day over baseline; moderate increase in ostomy output compared to baseline; limiting instrumental ADL)	 Consult with GI specialist Stool evaluation, imaging and endoscopy as clinically indicated Symptomatic treatment (loperamide, hydration, diet) Commence steroids (0.5-1mg/kg per day of prednisone or i.v. equivalent) until symptoms improve 	Interrupt spartalizumab/LAG525 until diarrhea recovers to Grade ≤1 or baseline

Permanently discontinue

spartalizumab/LAG525

Grade 4: Lifethreatening

consequences; urgent

intervention indicated

Diarrhea/Colitis (NCI-CTCAE v5.0) **Recommended Adverse Event Mandatory Dose** Grade **Modification requirements** management guidelines and/or abdominal pain/ to Grade 1, particularly in case of mucus or blood in stool. persisting/worsening symptoms. ulcerations or bleeding seen on endoscopy, or blood in stool. If no improvement occurs within days, manage as per Grade 3. Slowly taper steroids once symptoms improve to Grade 1 (ie. Over 4-6 weeks) Consider hospitalization; rule out bowel perforation and initiate i.v. hydration as needed. Consultation with gastroenterologist and consider endoscopy and biopsy. In addition to symptomatic Grade 3 Diarrhea: treatment initiate treatment with i.v. Increase of ≥7 stools per steroids (1 to 2 mg/kg/d of day over baseline;; methylprednisolone or equivalent) hospitalization indicated; Consider antibiotics as appropriate Interrupt severe increase in spartalizumab/LAG525 If no improvement in 2-3 days: ostomy output compared until diarrhea/colitis consider initiating infliximab 5mg/kg to baseline; limiting selfrecovers to Grade ≤1 or and continue steroids. (Infliximab is care ADL; baseline contraindicated in participants with sepsis/ perforation). Grade 3 Colitis: Severe Slowly taper steroids once abdominal pain: symptoms improve to Grade 1 (4 to peritoneal signs 6 weeks) If symptoms worsen during steroid reduction, initiate a re-tapering of steroids starting at a higher dose of 80 or 100 mg followed by a more prolonged taper and administer infliximab.

Same as Grade 3

Abnormal liver function tests		
Severity	Recommended Adverse Event management guidelines	Mandatory Dose Modification requirements

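### Three mandatory Grade 2 cells in Protocol Table 6-10 name only spartalizumab (PDR001), so read literally they require no LAG525 hold at Grade 2 onset in Arm 3

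*Protocol*

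**What the plan says.** Table 6-10 (Protocol 6.5.1.2.1) is headed "Table 6-10 Criteria for dose interruption and re-initiation of LAG525 and spartalizumab treatment for" other potential immune-related events of special interest. Its mandatory column gives these Grade 2 instructions:

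- Acute pancreatitis: "Grade 2 acute pancreatitis: Interrupt PDR001 until recovery to ≤ Grade 1 or baseline".
- Myasthenia gravis: "Mandatory Dose Modification requirements • Interrupt PDR001 until" recovery. The column header runs into the cell in the extracted text, but the drug named is clear.
- The row that calls for an ophthalmologist: "Grade 2 Interrupt PDR001 until recovery to ≤ Grade 1 or baseline Grade 3 and 4 Permanently discontinue". The row label and the drug name after the last word are lost. Uveitis is in the table's list of events, so this is presumably that row.

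For higher-grade pancreatitis the same column reads "Grade ≥3 acute pancreatitis: Permanently discontinue spartalizumab/LAG525", and the myasthenia gravis cell likewise stops both antibodies at Grade 3 or above.

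Section 6.5.1.2.1 makes the dose-modification column binding and the management column advisory. Section 6.5.1.1 adds that departures from mandatory interruptions are not permitted. Section 1.1.3.2 identifies PDR001 as spartalizumab, and Section 3 defines Arm 3 as LAG525 with carboplatin.

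**The concern.** In a binding column, the drug named decides what a site must do. LAG525 is the only checkpoint inhibitor in Arm 3. A site that follows these three cells to the letter finds an instruction to interrupt a drug the participant is not receiving, and no instruction about the one that could be causing the event. At stake is whether a Grade 2 immune event of these kinds must lead to a LAG525 hold at onset or is left to judgement. The point concerns participant safety and consistent conduct across arms, not an estimate or a test.

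**Working it through.** No figure in the plan needs reproducing. The check has three parts.

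**1. Are these cells out of line with the rest?** Mandatory interruption cells in Tables 6-3 to 6-10, leaving out cells that only ask the investigator to consider interruption:

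| Table | Names both antibodies | Names PDR001 only |
|---|---|---|
| 6-3 diarrhea/colitis | 2 (Grades 2, 3) | 0 |
| 6-4 liver | 1 (Grade 2) | 0 |
| 6-5 skin | 2 (Grade 2 for specified severe reactions; Grade 3) | 0 |
| 6-6 nephritis | 1 (Grade 2) | 0 |
| 6-7 pneumonitis | 1 (Grade 2) | 0 |
| 6-8 endocrine | 2 (symptomatic endocrinopathy; autoimmune diabetes) | 0 |
| 6-9 infusion reactions | 0 | 0 |
| 6-10 other events | 1 (general Grade 3 row) | 3 |
| Total | 2+1+2+1+1+2+0+1 = 10 | 3 |

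The usual form is that of Table 6-3 at Grade 2: "Interrupt spartalizumab/LAG525 until diarrhea recovers to Grade ≤1 or baseline". The only cells that depart from it are the three at issue.

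**2. Does another rule force a LAG525 hold at Grade 2 onset in Arm 3?**

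- General Grade 2 row of Table 6-10: names both antibodies, but only asks that interruption be considered.
- Default interruption in 6.5.1.1: limited to events absent from the tables. These events are listed.
- All-drug delay in 6.5.1.1: starts once an event requires interruption of a study drug. Read literally, no such requirement exists in Arm 3. The delay is also worded as advice and runs for at most 2 weeks.
- Steroid hold in 6.5.1.2.2: binding on LAG525, but only while prednisone cannot be brought below 10 mg/day before the next dose. Starting steroids is itself advisory. For pancreatitis the advice is firm ("Initiate steroids in case of ≥ grade 2 acute pancreatitis"); for myasthenia gravis they are to be considered; the surviving ophthalmologist text gives no steroid instruction. Where steroids are used, the suggested complete taper is at least 4 weeks (4 × 7 = 28 days) against a 21-day cycle, so the hold would usually catch a LAG525 dose.
- Permanent discontinuation rules in 6.5.1.2.1 for a persistent event or failure to reduce steroids: these act at 12 weeks, not at onset.
- Assuming that all drugs contribute when causality is unclear (6.5.1), and stopping treatment believed to harm the participant (9.1.1): both depend on the investigator's judgement.

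None of these is an unconditional requirement at Grade 2 onset.

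**3. Who is affected?** From the Amendment 4 summary: 20 + 34 + 34 = 88 randomised and 85 off treatment, so 88 − 85 = 3 on treatment, all in Arm 2. Arm 3 therefore had 0 of 34 on treatment. The documents give no event rates for these conditions in this setting; 6.5.1.2.1 describes events of this kind as rare.

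**The case against.** The strongest reply is that the slip has almost no practical reach. No Arm 3 participant was on treatment at Amendment 4, and the sponsor had ended LAG525 development in this disease. Exclusion criteria 9 and 11 keep out recent acute or any chronic pancreatitis and, with exceptions, active autoimmune disease. The general Grade 2 row does address LAG525, and a discretionary Grade 2 standard is also all that the visible text offers for other listed events such as autoimmune neuropathy, vasculitis and myositis. All of this stands and limits the severity. It does not make the three cells right: for these events the table chose a mandatory hold and then named a drug that one arm does not receive.

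It could also be argued that the wording is deliberate, since 6.5.1 says recommendations are made per drug for compound-specific toxicities. The table title and the higher-grade text point the other way, because for myasthenia gravis and pancreatitis both antibodies are stopped at Grade 3 or above.

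A reader might infer more than the documents support:

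- That Arm 3 is unprotected at Grade 2. It is not; the safeguards above reach LAG525, though conditionally or by discretion.
- That Arms 1 and 2 share the gap. There the PDR001 hold triggers the all-drug delay, and 6.5.1.1 handles the two antibodies as one unit, so LAG525 is largely covered.
- That 34 participants were exposed to a faulty rule. Earlier protocol versions are not supplied, and nobody in Arm 3 was being treated at Amendment 4.
- That every mention of PDR001 alone in the table should change. The management note "PDR001 may be continued in case of asymptomatic, isolated enzyme elevations without evidence for pancreatitis" is permissive, so omitting LAG525 from it leaves no hold missing.

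**Conclusion.** The inconsistency is real and minor. Three of the thirteen mandatory interruption cells name only spartalizumab, and in Arm 3 this leaves no compulsory LAG525 interruption at Grade 2 onset of myasthenia gravis, acute pancreatitis or the ophthalmologist-row event. The conclusion rests on a literal reading of a binding column and, for the third row, on the presumption that it is uveitis; the pancreatitis cell is fully legible and carries the point by itself. The intended meaning is recoverable, pancreatitis would usually be covered by the steroid hold if the steroid advice is followed, and no endpoint is affected. The documents do not support a claim that any participant was harmed or wrongly dosed.

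**What to change.** In Table 6-10, replace PDR001 with spartalizumab/LAG525 in the three Grade 2 mandatory cells: myasthenia gravis, acute pancreatitis and the ophthalmologist row.

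Leave the note on isolated enzyme elevations unchanged. Extending it would newly permit LAG525 dosing through such elevations. Section 1.1.3.1.2 reports Grade 3 elevated lipase as a dose-limiting toxicity of single-agent LAG525, and Grade 3 or 4 amylase and lipase increases suspected to be treatment-related in 2 participants each. Without the extension, the 6.5.1.1 default may require a hold. Whether to permit dosing is a clinical decision that the documents do not settle.

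The cost is one drug name in three cells, made through a written amendment approved by the sponsor, by Health Authorities where required, and by the IRB/IEC (Section 14.1). With nobody in Arm 3 on treatment, it can wait for the next amendment, or be carried into any later protocol that reuses this table. Data collection and analysis do not change.
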